CLINICAL TRIAL PROTOCOL: NE3107-TRP-001

Study Title: A Phase II Open-Label Study for the Use of Anti-Inflammatory, Insulin-Sensitizing NE3107 for Treatment of Cognitive Decline Due to Degenerative Dementias

Study Number: NE3107-TRP-001

Study Phase: 2

Product Name: NE3107 (17a-ethynyl-androst-5-ene-3b,7b,17b-triol)

IND Number: 159271

Indication: Degenerative Dementias

Investigators: Principal Investigator: **[name], M.D., F.A.A.N.**
Sub-Investigator: [name], M.D.

Sponsor: The Regenesis Project

Sponsor Contact: [name]

Sponsor's Legal Representative: [name], ND, JD
[name]
[name]

Medical Monitor: [name]

Original Protocol:	11/04/2021
Amendment 1:	Version 2, dated 12/17/2021

Confidentiality Statement

This document and its contents are the property of and confidential to [name] Inc. dba The Regenesis Project. Any unauthorized copying or use of this document is prohibited.

SYNOPSIS

Sponsor: [name] MD Inc., dba The Regenesis Project

Name of Finished Product: NE3107

Name of Active Ingredient: 17a-ethynyl-androst-5-ene-3b,7b,17b-triol

Study Title: A Phase II Open-Label Study for the Use of Anti-Inflammatory, Insulin-Sensitizing NE3107 for Treatment of Cognitive Decline Due to Degenerative Dementias

Study Number: NE3107-TRP-001

Study Phase: 2

Primary Objective(s):

Primary endpoints will involve a comparison of neurophysiological health as evaluated by multi-modal brain MRIs obtained at baseline and post-intervention termination (3 months).

Secondary Objective(s):

Secondary endpoints will include a longitudinal comparison of cognitive functioning as well as serological inflammatory markers and glucose and insulin homeostasis.

Study Design:

The present open label study is designed to evaluate the potential efficacy of NE3107 among patients with degenerative dementias through neuroimaging, cognitive performance testing, and serological measures of insulin resistance.

Study Population:

Approximately 25 participants are planned to be enrolled in this study.

Diagnosis and Main Criteria for Inclusion

Inclusion criterion are a diagnosis of cognitive decline due to degenerative dementia and a clinical dementia rating (CDR) score of 0.5 or 1.

Test Product; Dose; and Mode of Administration:

NE3107 20mg BID

Duration of Treatment:

The duration of active intervention will be three (3) months.

Pharmacokinetic Variables:

C _{max}	Maximum concentration of drug in plasma or serum
CNS	Central nervous system
cPLA ₂	phospholipase A2
CRP	C-reactive protein
C-SSRS	Columbia-Suicide Severity Rating Scale
CXCL	C-X-C motif chemokine ligand
CYP	Cytochrome P450
EAE	experimental autoimmune encephalomyelitis
EC ₅₀	half maximal effective concentration
ECG(EKG)	Electrocardiogram
eGFR	Estimated glomerular filtration rate
ERK1, ERK2	extracellular signal regulated kinase 1 and 2
F(%)	Percent absolute oral bioavailability

Abbreviation	Definition
GABA	gamma amino butyric acid
GD	Gestation day
GDS-SF	Geriatric Depression Scale Short Form
GLP	Good laboratory practice
GRK	G protein-coupled receptor kinase
HbA1c	hemoglobin A1c
HDL	High-density lipoprotein
HE3129	3 β ,7 β -dihydroxy-androst-5-en-17-one
HE3291	17 α -ethynyl-androst-5-ene-3 β ,7 α ,17 β -triol
HE3393	17 α -ethynyl-3 β ,17 β -dihydroxy-androst-5-en-7-one
HE3892	17 α -ethynyl-androst-5-ene-2 α ,3 β ,7 β ,17 β -tetrol
HE3545	17 α -ethynyl-androst-5-ene-3 α ,7 β ,17 β -triol
HE3633	17 α -ethynyl-17 β -hydroxy-androst-4,6-diene-3-one
hERG	Human-ether a-go-go related gene, Kv11.11 alpha subunit of potassium ion channel
HIS	Hachinski Ischemic Scale
HOMA	Homeostatic model assessment
HPA	hypothalamus-pituitary-adrenal
HPLC	High-performance liquid chromatography
Hsd17b4	17 β -hydroxysteroid dehydrogenase 4
IFN	interferons
I κ B	inhibitor of NF κ B
IKK	I κ B kinase
IL	interleukin cytokines
IGT	impaired glucose tolerance
IQGAP1	IQ Motif Containing GTPase Activating Protein 1 scaffold
IQR	inter-quartile range
IR	Insulin resistance
iv	intravenous
JNK	c-Jun N-terminal kinases
κ B	promoter NF κ B transcription site
KO	Knock out
KSR	kinase suppressor of Ras (scaffold)
LC-MS-MS	Liquid chromatography-tandem mass spectrometry
LDL	Low-density lipoprotein
LID	L-dopa induced dyskinesia
LPS	lipopolysaccharide
Lrp1	low density lipoprotein receptor related protein

Abbreviation	Definition
MEK	mitogen-activated protein kinase kinase (phosphorylates ERK)
MAP3K8	mitogen-activated kinase kinase kinase (phosphorylates MEK; Tpl2 in mouse, COT1 in human)
MAPK	mitogen-activated protein kinases
MAPK1	p42 ERK2
MAPK3	p44 ERK1
MCI	Mild cognitive impairment
MCP1	monocyte chemoattractant protein 1
mITT	Modified Intent-to-Treat
MPK1	mitogen-activated protein kinase phosphatase 1
MMP	matrix metallopeptidases
MMSE	Mini mental state exam
MNK	MAP kinase signal-integrating kinase
MP1	Mitogen-activated protein kinase scaffold protein 1
MORG	WD-repeat protein family scaffold
MPTP	1-methyl-4-phenyl-1,2,3,6-tetrahydropyridine
MRI	Magnetic resonance imaging
mRNA	messenger ribonucleic acid
MSK	stress-activated protein kinase
MTD	Maximum tolerated dose
M value	mean glucose infusion rate
MW	Molecular weight
NE3107	17 α -ethynyl-androst-5-ene-3 β ,7 β ,17 β -triol
NOAEL	No-observed-adverse-effect-level
NEMO	NF- κ B essential modulator (aka IKK γ)
NF κ B	nuclear factor kappa-light-chain-enhancer of activated B cells
NMT	Not more than
Nos	Nitric oxide synthase
NPI-12	Neuropsychiatric Inventory 12-Domain
p-	phospho substituent (e.g. p-ERK)
p38	p38 MAPK
p65	NF κ B3
p105	NF κ B subunit
Paxillin	scaffold encoded by the PXN gene
PBMC	Peripheral blood mononuclear cells
PD	Parkinson's disease
PD98059	MEK inhibitor
PEA-15	proliferation and apoptosis adaptor protein-15

Abbreviation	Definition
PgP	P-glycoprotein
PK	pharmacokinetics
PK-PD	Pharmacokinetics-pharmacodynamics
po	Oral route of drug administration
PPAR	peroxisome proliferator activated receptors
QD	Once daily
QSAR	Quantitative structure-activity relationship
QT interval	Length of time from the start of the Q wave to the end of the T wave, the time taken for ventricular depolarization and repolarization
Raf	serine/threonine-specific protein kinases
Ras	small GTPase proteins involved in signal transduction
RAW264.7	mouse macrophage cell line
RH	Relative humidity
Rsp6ka3	p90 ribosomal S6 kinases
SAE	Severe adverse event
Sef	similar expression to fgf genes scaffold
SIRT2	sirtuin-2
SP1	specificity protein 1 (transcription factor)
t _{1/2}	Half-life
T2D	Type 2 diabetes
TG	Triglycerides
T _{max}	Length of time after drug administration to C _{max}
TLR	toll-like receptor
TNF	tumor necrosis factor
UC	Ulcerative colitis
ULN	Upper limit of normal
USP	United States Pharmacopeia
Vcam	vascular cell adhesion molecules
V _d	Volume of distribution

1 INTRODUCTION

Considering how many people are in a state of mild cognitive impairment (MCI) and frank dementia, there is a substantial cost to society in terms of financial burden and suffering (Connolly, 2018). Degenerative conditions that result in cognitive change in middle and late life are frequently associated with abnormal deposits of protein material (e.g., amyloid, phospho-tau) which interfere with neuronal function and viability (Lacor, Buniel, Furlow, Clemente, Velasco, Wood, et al., 2007; Khan, 2016). Inflammation and insulin resistance in the CNS and abnormal protein deposition and resultant physiological impairment characterize conditions of the Alzheimer's dementia (AD) type (Kinney, Bemiller, Murtishaw, Leisgang, Salazar & Lamb, 2018; Rorbach-Dolata & Piwowar, 2019).

Neuroinflammation prompts AD progression, impaired cholesterol efflux and reduced insulin signaling (insulin resistance) (Hölscher, 2020; Kinney et al., 2018; Rorbach-Dolata & Piwowar, 2019; Chow, Shi & Cheng, 2019). Insulin resistance has been considered a risk factor as well as a feature of AD, and has also been associated with increased $\alpha\beta$ -42 secretion, neuritic plaque burden, abnormal insulin receptor performance, decreased glucose metabolism, and consequently decreased cognitive performance (Hölscher, 2020; Chow et al., 2019; Reading & Ahlem, 2021).

No therapy exists that has been proven to halt or reverse the progressive deposition of abnormal proteins or the attendant neurophysiological deterioration. Various investigational therapies aim to target the pathophysiological processes of AD; from combating abnormal protein deposition, to targeting sources of systemic and neuroinflammation, to providing cholinergic, hormonal, and metabolic support. A promising area of research is the ongoing use of insulin synthesizers as a therapeutic option for AD. Several Phase 3 studies have been initiated and/or completed with compounds such as Semaglutide, a hormone that stimulates insulin signaling (Nauck, Quast, Wefers, & Meier, 2020), Metformin, an insulin synthesizer (Koenig, Mechanic-Hamilton, Xie, Combs, Cappola, Xie, et al., 2017; Lin, Wang, Ma, Wang, Gong, Zhang, et al., 2018), and NE3107, an anti-inflammatory insulin-sensitizing agent (Reading & Ahlem, 2021).

In this study, the drug under investigation is NE3107 (17a-ethynyl0androst-5-ene-3b, 7b, 17b-triol). NE3107 is a small, blood-brain permeable molecule with anti-inflammatory and insulin-sensitizing properties. The mechanism of action for NE3107 involves selective inhibition of inflammatory mediators.

This study seeks to measure changes in advanced neuroimaging, CNS biomarkers of Alzheimer's disease, inflammatory serological and metabolic parameters, and cognitive performance measures among participants treated with NE3107.

The dose of NE3107 administered in this study will be 20 mg BID. Nonclinical safety studies and prior clinical trials have not identified a toxicity indicating the need for exploration of dose response. NE3107 dose response for anti-inflammatory and insulin sensitizing activity was not statistically resolved between 2, 5 and 10 mg BID in impaired glucose tolerance subjects in trial HE3286-0102. Neither preclinical data, nor available clinical information suggest an ordered dose response relationship across exposure on key indices of glycemic

control and insulin sensitivity. There has been no indication that NE3107's anti-inflammatory activity could be increased with higher exposures. The dose duration will be 3 months. The rationale for 3-month administration is to allow sufficient time for detectable change to occur. The route of administration for NE3107 will be orally. NE3107 is formulated with common excipients used in oral medications in #2 hard gelatin capsules. NE3107 capsules are stable at room temperature for at least 18 months.

2 STUDY OBJECTIVES

2.1 Primary Objective(s)

Primary endpoints will involve a comparison of neurophysiological health as evaluated by multi-modal brain MRIs obtained at baseline and post-intervention termination (3 months). Specifically, multi-modal MRI endpoints will include: (1) An increase or stabilization in glutathione levels (as measured by magnetic resonance spectroscopy, MRS) compared to baseline. Patients with cognitive decline often show characteristic change in MRS or volumetric evaluation compared to age-matched controls (Kuhn et al. 2021); (2) Stabilized and/or improved dendritic density compared to baseline (as measured by diffusion tensor imaging, DTI-NODDI); (3) Enhancement of arterial signal compared to baseline (as quantified by arterial spin labeling, ASL). Patients with cognitive decline often have decreased perfusion in temporal parietal or frontal regions of the brain with ASL perfusion (Kuhn et al. 2021); (4) increased functional connectivity of the nucleus basalis of Meynert (NBM) with both hippocampi as well as between both hippocampi compared to baseline, as visualized by seed analysis of blood-oxygen level dependent (BOLD) imaging as well as (5) increased neurovascular coupling as visualized by BOLD compared to baseline.

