By measuring free-water changes and the integrity of white matter tracts, DTI can indirectly measure changes caused by amyloid plaque deposition (Wen, Risacher, Xie, Li, Harezlak, Farlow et al., 2021; Alexander, Lee, Lazar & Field, 2007; Smith, Johansen-Berg, Jenkinson, Rueckert, Nichols, Miller et al., 2007). The post-NE3107 DTI metric [fractional anisotropy (FA) and mean, axial and radial diffusivity (MD, AD, RD)] image will be subtracted from the baseline image to produce change images (Fu, Shrestha, Sun, Wu, Luo, Zhang, et al., 2019). Neurite orientation dispersion and density imaging (NODDI) uses a three-compartment model to probe brain tissue microstructure: (1) Free Water Fraction (FWF) which estimates the extent of CSF contamination, (2) Neurite Density index (NDI) which quantifies the packing density of axons/dendrites, and (3) Orientation Dispersion index (ODI) which assesses the coherence of neurites (Fu et al., 2019; Zarei, Patenaude, Damoiseaux, Morgese, Smith, Matthews et al., 2010).

Limited literature using NODDI has been produced in-vivo in mild-cognitive impairment subjects, but the current results show it to be more sensitive/robust than traditional FA values (Fu et al., 2019). Similar to ASL, the three indexes will be compared between baseline/follow-up values. It would be expected that an increase in NDI and a decrease in ODI/FWF to correspond with an improvement in brain health (Fu et al., 2019). Here, an established tract-based spatial statistics (tbss) approach will be used to assess the relationship between voxel-wise changes in white matter integrity (Fu et al., 2019). Additionally, graph theory will be applied to quantify the effect of NE3107 on hippocampal connectivity and associate this effect with cross-sectional and longitudinal cognitive performance (Wen et al., 2021). Lastly, probabilistic tractography will be used to simulate white matter connectivity

between the hippocampus formations (Zarei et al., 2010) and Nucleus Basalis of Meynert. The baseline and follow-up will similarly be compared. Again, RMANOVA will compare pre-and post-NE3107 treatment and within group analyses will assess network predictors of response to NE3107 treatment. All imaging analyses will be corrected for multiple comparisons, both across voxel and between analyses.

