Arterial Spin Labeling (ASL) data will be processed and analyzed using FSLs Bayesian Inference for ASL MRI (BASIL; Chappell, Groves, Whitcher & Woolrich, 2009; Woolrich, Chiarelli, Gallichan, Perthen & Lie, 2006). ASL scans yield a perfusion image with voxel values representing local perfusion rates; perfusion difference will be calculated (subtracting tagged/control pairs) and averaged to create a mean perfusion-weighted image (Chen, Wolk & Reddin, 2011). Quantification to cerebral blood flow (CBF) values (milliliters of blood per 100 g of tissue per minute) will be implemented using an estimate of the equilibrium magnetization of arterial blood and the mean perfusion values (Ahlgren, Wirestam, Knutsson & Petersen, 2018; Hernandez-Garcia & Jahanian, 2010). Given the variability of ASL across patients, CBF data will be examined as a ratio to mean grey matter signal.

Each participant's ASL data will be linearly registered to each his or her T1-weighted image; images will then be transferred to MNI space using non-linear registration in FSL. Within FSL, a voxel-wise between groups (normal vs MRI) comparison of perfusion, corrected for multiple comparisons, will be performed. A repeated measures comparison within subject for pre-vs post intervention ASL as well as between groups will be used to compare effects of NE3107 to normals. Demographic covariates will be included in the model as indicated. All imaging analyses will be corrected for multiple comparisons, both across voxel and between analyses.

Existing literature consistently demonstrates a dropout of signal seen in the temporal parietal lobes among individuals with dementia of the probable Alzheimer's type (Zhang, Gordon & Goldberg, 2017). The mean perfusion values per voxel in the temporal parietal regions will be measured and used to generate a statistical output of participant values relative to a normative, age-matched database. This will test the hypothesis that there will be either stabilization or improvement of voxel signal among participant scans compared with the normative database associated with NE3107.

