Further, BOLD-activity changes will be assessed within a standard ROI (e.g., hippocampus; conventionally defined using a priori anatomic segmentation). To do so, the percent signal change within the same ROI across multiple scan acquisitions will be extracted to compare an individual participant's change relative to expected levels of change. The degree of this change will be correlated with NE3107 treatment and other neural network and behavioral changes to further elucidate the intricacies of the NE3107 treatment. A decrease in neurovascular coupling is expected (as shown and evaluated voxel-wise) globally and regionally in the locus coeruleus and temporal parietal lobes compared to age-matched controls. With NE3107 intervention, it is hypothesized that participants will yield improvement in neurovascular response from baseline. This will be analyzed relative to the normative database and expected decline.

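### Stabilization counts as success for two primary MRI endpoints, and for ASL in section 9.5.1, but no margin or rule says how it would be shown

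*Combined protocol and SAP*

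**What the plan says.** Section 2.1 lists five primary MRI endpoints, and section 9.5 repeats them. Two admit no change as success: glutathione, "An increase or stabilization in glutathione levels (as measured by magnetic resonance spectroscopy, MRS) compared to baseline", and NODDI, "Stabilized and/or improved dendritic density compared to baseline". The other three are worded as a gain from baseline. Among them are ASL, "Enhancement of arterial signal compared to baseline", and neurovascular coupling, "increased neurovascular coupling as visualized by BOLD compared to baseline".

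Section 9.5.1 treats ASL differently. It plans "A repeated measures comparison within subject for pre-vs post intervention ASL" and a comparison with normals, and then states for temporal-parietal perfusion: "This will test the hypothesis that there will be either stabilization or improvement of voxel signal among participant scans compared with the normative database". For neurovascular coupling it hypothesizes improvement from baseline, but the next sentence reads "This will be analyzed relative to the normative database and expected decline".

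The analyses named are a Wilcoxon signed-rank test for glutathione and repeated-measures ANOVA for imaging generally and for NODDI (both section 9.5.1), and an MMRM as the primary efficacy model (section 9.1). The significance level is 0.05. Section 9.5.1 asks whether imaging improved, anticipates a rise in glutathione, and treats a rise in the neurite density index as favourable. Thresholds for meaningful change appear only in section 9.5.2, for secondary endpoints.

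**The concern.** A test of change can support a claim that a measure rose or fell. It cannot support a claim that a measure held steady unless the plan also says how large a decline must be excluded. Here stability is part of the success definition, while every planned analysis and every stated expectation concerns improvement.

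With about 20 completers, a non-significant result is quite likely even when there is a real decline. If it is then described as stabilization, a study that could not tell decline from no change is reported as having met a primary endpoint. For ASL the criterion also differs between sections, and for ASL and neurovascular coupling the deciding comparison is open. The choice could then be made after the data are seen.

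**Working it through.** **Step 1: the plan's own figure.** Section 9.2 plans 20 completers from 25 enrolled at 20% attrition: 20 / (1 − 0.20) = 25, which reproduces. The 20 cannot be rebuilt from 80% power and 0.05, because section 9.2 gives no effect size, SD, endpoint or test.

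**Step 2: wording side by side.**

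| Endpoint | Sections 2.1 and 9.5 | Section 9.5.1 |
|---|---|---|
| Glutathione | Rise or stable, versus baseline | Wilcoxon versus baseline; rise anticipated |
| Dendritic density | Stable and/or improved, versus baseline | Baseline versus follow-up; rise in density index regarded as favourable |
| ASL | Enhanced, versus baseline | Pre versus post, and stable or improved versus normative database |
| Hippocampal and basal-nucleus connectivity | Increased, versus baseline | No stabilization wording |
| Neurovascular coupling | Increased, versus baseline | Improvement from baseline hypothesized; analysed against normative database and expected decline |

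No cell supplies a margin or a rule for declaring stability.

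**Step 3: what the gap could allow.** Assumptions:
- stabilized is read as no significant decline;
- one scalar endpoint, such as glutathione;
- normally distributed changes and a paired t-test, two-sided 0.05;
- n = 20 completers;
- effects in SD of within-person change, because the documents give no SD and no expected MRI decline.

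The critical value is t(0.975, 19) = 2.093. The largest observed mean decline that is still non-significant is 2.093 / √20 = 0.47 observed SD.

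For a true decline d, P(no significant decline) = 1 − F(−2.093), where F is the non-central t distribution with 19 degrees of freedom and non-centrality −d√20.

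| True decline (SD) | Non-centrality | Endpoint met, paired t | Endpoint met, Wilcoxon (simulated) |
|---|---|---|---|
| 0.2 | −0.894 | 87% | 87% |
| 0.3 | −1.342 | 75% | 77% |
| 0.5 | −2.236 | 44% | 46% |

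Section 9.5.1 also promises: "All imaging analyses will be corrected for multiple comparisons, both across voxel and between analyses". Any stricter level widens the non-significant region and raises these percentages. Under this reading, a correction meant to make claims harder would make a stabilization claim easier.

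**Step 4: what a proper stability claim would need.** Require the lower limit of the two-sided 95% interval to lie above −m. With true change zero, power is 1 − F(2.093) with non-centrality m√20.
- m = 0.3 SD: 25% at 20 completers; 80% needs 90 completers.
- m = 0.5 SD: 56% at 20 completers; 80% needs 34 completers.
- The smallest margin with 80% power at 20 completers is about 0.66 SD.

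These figures do not describe the voxel-wise NODDI or ASL analyses.

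**The case against.** The strongest reply is that the plan never equates a non-significant result with stability. The tests have a null of no change and an alpha of 0.05. Section 9.1 declares formal significance only when a hypothesis and those before it in its family are significant. Section 9.5.1 expects improvement. All of this stands. A reader might infer that the plan instructs analysts to call a null result a success; the documents do not say so. What remains is narrower: the endpoint definition admits stability, nothing says how to show it, and nothing rules out the weak reading.

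Three other stronger readings also fail:
- *No multiplicity method is given.* Section 9.1 does describe a sequential gate, though without an order and directly after a sentence on the neuropsychological family. Section 9.5.1 adds an imaging correction that it does not name. No particular corrected level is therefore used here.
- *Baseline is replaced as comparator.* Section 9.5.1 keeps the pre-versus-post comparison for ASL and hypothesizes coupling improvement from baseline. The normative comparison is added.
- *A high pass rate at zero true change is an error.* Zero change is genuine stability. Only the pass rates under true decline show a problem.

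It is fair to say that the SD-unit figures rest on assumptions. The gap in the text does not depend on them.

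**Conclusion.** The concern holds in this limited form and should be fixed before data are seen. Two of five primary MRI endpoints, and the ASL hypothesis in section 9.5.1, include a stabilization criterion that has no matching test. ASL is also worded more loosely in 9.5.1 than in 2.1 and 9.5. For ASL and neurovascular coupling the plan does not say whether change from baseline or the normative comparison decides.

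The size is conditional. If stability were taken as no significant decline, real declines of 0.2 to 0.5 SD would pass between 87% and 44% of the time, given the assumptions in the working. The documents do not establish that such declines are expected or that this rule would be used.

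**What to change.** 1. In sections 2.1, 9.5 and 9.5.1, delete the stabilization wording for glutathione, dendritic density and ASL, so that success means improvement from baseline. Add: *A non-significant change is reported as inconclusive, with its confidence interval.*
2. If stabilization is kept, state in advance a justified decline margin for each endpoint, require the lower confidence bound to lie above it, and report the power at 20 completers as in step 4.
3. Reconcile sections 2.1 and 9.5 with 9.5.1 for ASL and neurovascular coupling: make change from baseline the primary comparison and the normative-database comparison descriptive.

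The cost is text edits, plus work to justify margins if stabilization is kept; no new data are needed. The downside is that fewer outcomes can be called a success, and at 20 completers only a wide margin is testable with good power. Even after the change, there is no control group (section 5.1.2), so the result describes change from baseline and does not by itself show a drug effect.
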